### **3.1.3 Treatment of 1 migraine attack within 10 weeks**

Throughout the treatment period, patients will record details of any AEs and medications taken in the diary provided.

If a migraine headache or attack occurs within 10 weeks of randomization (Visit 2), patients will treat it with 1 dose of study drug. Patients will record the details regarding the migraine headache using the diary provided, including AEs and medications.

### **3.1.4 Interim visit (4 weeks from randomization visit)**

If there is no treatment of a migraine headache or attack with the study drug within 4 weeks of randomization (Visit 2), patients will return to the study site to review dosing instructions. Detailed instructions for use of the paper patient diary will also be reviewed. Adverse events that occurred since the last visit will be reported. The interim visit will be captured in the electronic case report form (eCRF), and the visit date and confirmation that dosing and diary

instructions have been provided will be collected. The nasal spray training device will not be used at the interim visit.

### **3.1.5 Visit 3 (final visit/end-of-study) or early termination (ET) visit**

Visit 3 (final visit/end-of-study) will occur after patients have treated 1 migraine attack. Patients will return to the investigative site for the final study visit within 2 weeks after treating 1 migraine attack, or within 10 weeks after Visit 2 (randomization) if no migraine headaches or attacks are treated.

Patients who discontinue early from the study will undergo Visit 3 procedures at the early termination (ET) visit. The following procedures will occur at Visit 3 and at the time of discontinuation (ET visit) from the study:

- Vitals signs (seated BP and pulse, and oral body temperature);
- 12-lead ECG;
- Physical examination;
- Review of concomitant medications;
- Blood samples will be collected for laboratory assessments (clinical chemistry and hematology);
- Urine sample will be collected for urinalysis and pregnancy test (females only);
- Return of study drug nasal spray device;
- Review and return of paper patient diaries;
- Reporting of any AEs since Visit 2;
- C-SSRS to assess suicidal risk, ideation, and behavior.

**Table 1 Study plan**

Study procedures	Visit 1 (-Day 30 to Day 0)		Visit 2 (30±3 days after Visit 1) Day 0 Randomization	Migraine attack, treatment, and patient's diary recording	Interim visit if no study treatment 4 weeks from randomization a	Visit 3 Final visit after treating 1 attack or within 10 weeks after Visit 2 or ET
	Screening	Run-in period and placebo challenge				
Signed informed consent and assent forms	X					
Inclusion/exclusion criteria	X		X			
Demography	X					
Medical & relevant surgical history	X					
Migraine headache history	X		X			
Medications, prior b and concomitant	X	X c	X	X c		X
Physical examination	X					X
Height	X					
Weight	X					
Urine test for drug abuse	X					
Urine pregnancy test	X		X			X
Dispense placebo nasal spray device	X					
Dispense study drug nasal spray device			X			
Dose instructions	X		X		X	
Dispense patient diary	X		X			

**Table 1 Study plan**

Study procedures	Visit 1 (-Day 30 to Day 0)		Visit 2 (30±3 days after Visit 1) Day 0 Randomization	Migraine attack, treatment, and patient's diary recording	Interim visit if no study treatment 4 weeks from randomization a	Visit 3 Final visit after treating 1 attack or within 10 weeks after Visit 2 or ET
	Screening	Run-in period and placebo challenge				
Patient diary instructions	X		X		X	
Administer placebo nasal spray		X d				
Administer study drug nasal spray				X		
Patient enters diary data		X d		X		
Review and return of patient diaries, and record data on eCRF			X			X
Return placebo nasal spray device			X			
Return study drug nasal spray device						X
Safety assessments						
Vital signs (seated BP and pulse, oral body temperature)	X					X
12-lead ECG	X					X
Laboratory assessments (clinical chemistry, hematology, urinalysis)	X					X
AE reporting		X c	X	X c	X	X

**Table 1 Study plan**

Study procedures	Visit 1 (-Day 30 to Day 0)		Visit 2 (30±3 days after Visit 1) Day 0 Randomization	Migraine attack, treatment, and patient’s diary recording	Interim visit if no study treatment 4 weeks from randomization a	Visit 3 Final visit after treating 1 attack or within 10 weeks after Visit 2 or ET
	Screening	Run-in period and placebo challenge				
Rating scale						
C-SSRS	X		X			X

BP blood pressure; ET early termination.

[figure not shown]
a Patients will return for the interim visit to review study instructions. Visit date and confirmation that dosing and diary instructions were provided will be documented on the eCRF. The nasal spray training device will not be used at the interim visit.

b For 1 year (12 months)

c Concomitant medications and AEs collected in patient diary

d Patients will receive instructions for placebo nasal spray and patient diaries in order to complete the run-in and placebo challenge portion of the study.

**Figure 1 Study flow chart**

### 3.2 Rationale for study design, doses and control groups

The study design was selected because it is an easy, simple design of high quality and interpretable results. Adolescents must be aged 12 to 17 years at the time of screening and will not be enrolled if they turn 18 years of age at the time of randomization. This is consistent with the FDA guidelines.

Patients must be able to differentiate between migraine and non-migraine headaches to ensure they are able to participate in the protocol. Patients with a history of a minimum of 2 migraine attacks (moderately or severely disabling) per month are included to maximize the chance of a migraine occurring during the study period.

To address the differences in migraine diagnosis between adolescents and adults, this study will use both the International Headache Society (IHS) and International Headache Society-Revised (IHS-R) (Winner et al 1997) criteria in the inclusion criteria. As patients mature, their migraines become more adult-like, thus the use of both criteria will capture the appropriate population across the age range. IHS-R is the most robust diagnostic tool, incorporating the expanded symptoms complex for pediatric and adolescent migraine. If a patient satisfies the IHS criteria, then by definition he/she will satisfy the IHS-R criteria.

Doses of 0.5, 2.5, and 5 mg of zolmitriptan nasal spray have been selected for this trial. Patients are randomized to the different treatment arms with different probabilities. It is believed that the probability to show a treatment effect is greatest for the zolmitriptan 5 mg treatment arm; hence, this treatment arm is powered with 80% to be able to detect a true difference of 0.11 between placebo and zolmitriptan 5 mg. However, in order to be able to perform the study with a reasonable number of centers, the 2 other zolmitriptan arms are powered at a lower power, ie, 67% power to detect a treatment difference of 0.11 versus placebo. It is anticipated that the true treatment difference with an effective dose might be as large as 0.15 with this study design, including the enriched population obtained by the enrollment period and placebo challenge treatment. With a true difference of 0.15, there will be 90% power to detect a difference for the 2 lower doses compared with placebo and 96% power for zolmitriptan 5 mg versus placebo.

The pharmacokinetics in adolescents of nasally administered zolmitriptan has been evaluated (Trial D122100004). A 5 mg dose of zolmitriptan nasal spray in both male and female adolescents has similar area under the plasma concentration curve (AUC), maximum plasma (peak) drug concentration after single-dose administration ( $C_{max}$ ), and clearance as the adult population; and therefore, similar drug exposure as in the adult population.

Dosing in adolescents is generally based on body mass index (BMI) and weight as this ensures a relatively standardized population.

The rationale for the primary objective is to demonstrate that the effect of zolmitriptan is superior to placebo after single-dose administration in the acute treatment of migraine headache in adolescents between 12 to 17 years of age. The 2-hour pain-free endpoint is the IHS recommended primary outcome in guidelines for migraine studies. This ensures migraine headache relief of appropriate duration. The endpoints for the secondary objectives are commonly used endpoints in migraine studies. Endpoints collected before and after the 2-hour timepoint are included to support the primary endpoint.

Placebo is used as the comparator since the primary objective is to evaluate the efficacy of zolmitriptan.

Baseline assessments of headache intensity and associated symptoms are included as they are needed for derivation of the endpoints.

There is no evidence of a link between triptan use and suicidal behavior. Recent research studies have noted the increased risk of suicidality in frequent adolescent migraineurs. It is important to understand if treatment affects these symptoms when present. The C-SSRS ([Posner et al 2007](#)) will be performed to assess this.

No safety monitoring committee will be required since there are no specific safety concerns. Safety will be monitored on an ongoing basis and will include AEs, vital signs, laboratory assessments, ECG, and the C-SSRS to assess suicidal risks prior to and after treatment.

An external Data Monitoring Committee (DMC) consisting of an independent statistician will perform the interim analysis for sample size re-estimation based on blinded data only. The DMC will decide on the total sample size needed for the study.

## **4. SUBJECT SELECTION CRITERIA**

The investigator(s) should keep a record, the patient screening log, of patients who entered pre-study screening.

Each patient should meet all of the inclusion criteria and none of the exclusion criteria for this study. Under no circumstances can there be exceptions to this rule.

### **4.1 Inclusion criteria**

For inclusion in the study, patients must fulfill all of the following criteria:

1. Parent or legal guardian is able to provide written informed consent and patient is able to provide written assent.
2. Adolescents aged 12 to 17 years at the time of screening; patients must not be enrolled if they will turn 18 years of age within 10 weeks after randomization (Visit 2).
3. An established diagnosis of migraine (history indicating the presence of migraine for at least 1 year) with or without aura as defined by the IHS or IHS-R criteria. Patients with medical history of migraine for at least 1 year prior to screening as defined by IHS or IHS-R criteria without a historic documentation of migraine may be considered for entry after the history has been established and discussed with the medical monitor.
4. A minimum of 2 migraines, considered to be moderately/severely disabling, per month (by history);
5. A medical history of usual untreated migraine duration of  $\geq 3$  hours for any 3-month period prior to screening (Visit 1);
6. A history of migraine attacks occurring at intervals of  $>24$  hours apart, which is confirmed by medical history;
7. Have the ability to differentiate between migraine and non-migraine headaches;
8. All females in a relationship capable of producing a pregnancy should use a highly effective form of birth control. All females will have a pregnancy test. They must have a negative urine pregnancy test and confirmed (by the investigator) use of a highly effective form of birth control. The highly effective form of birth control includes, but is not limited to, total sexual abstinence, a vasectomized male partner

with confirmation of azoospermia plus condom, female sterilization by tubal occlusion plus condom, intrauterine devices (IUD, ie, copper banded coils plus condom, intrauterine systems (IUS, ie, levonorgestrel [eg, Mirena] plus condom), Depo-Provera plus condom, etonogestrel implants (eg, Implanon, Norplant, Nuva ring) plus condom, Ortho Evra plus condom, normal and low-dose combined oral contraceptives plus condom, norelgestromin/ethinyl estradiol (EE) transdermal system plus condom, intravaginal device (eg, EE and etonogestrel) plus condom, and Cerazette (desogestrel) – currently the only highly effective progesterone-based pill – plus condom. A diaphragm and foam or condom or sponge and condom are not acceptable. Females should be on a stable method of birth control for a minimum of 3 months prior to study entry.

9. Absence of clinically significant abnormalities indicated from the medical history, physical examination, laboratory assessments (clinical chemistry, hematology, urinalysis), and urine drug screen results;
10. Clearly understands and is likely to comply with all study procedures and scheduled visits, as demonstrated during the run-in and placebo challenge period;
11. Ability to read and write and use the patient diary;
12. The investigator believes participation in the study will not be harmful to the patient.

#### **4.2 Exclusion criteria**

Patients must not enter the study if any of the following exclusion criteria are fulfilled:

1. Involvement in the planning and/or conduct of the study (applies to both AstraZeneca staff and/or staff at the study site);
2. Had previous randomization of treatment in this study;
3. Is currently participating or has participated in another clinical study within 30 days prior to screening for this study;
4. Any medical condition that may put the patient at increased risk with exposure to zolmitriptan or that may interfere with the safety or efficacy assessments (in the opinion of the investigator);
5. A history of basilar, ophthalmoplegic, or hemiplegic migraine headache or any potentially serious neurological condition that is associated with headache;
6. Had an unacceptable adverse experience following previous use of any 5HT1B/1D agonist drug (in the opinion of the investigator);

7. Evidence of ischemic heart disease, arrhythmia (eg, atrial fibrillation or flutter, frequent premature ventricular contractions, atrioventricular block), accessory conduction pathway disorder (eg, Wolff-Parkinson-White syndrome) as determined by central cardiologist using predetermined and agreed upon pediatric standards;
8. History, symptoms, or significant risk factors for ischemic heart (eg, silent ischemia, angina, myocardial infarction) or other cardiovascular disease, including coronary vasospasm, cardiac accessory conduction pathways, arrhythmias, cerebrovascular syndromes (eg, stroke), or peripheral vascular disease;
9. Clinically significant abnormalities indicated from the medical history, physical examination, clinical chemistry, hematology, and urine drug screen (eg, stable diabetes mellitus would not qualify as a clinically significant abnormality for the purposes of this study);
10. Had a diagnosis or suspicion of drug-induced or chronic daily headaches within 1 year;
11. Has 14 or more non-migraine headache days each month for 3 months before the screening visit;
12. Has uncontrolled hypertension defined as systolic or diastolic BP that exceeds the 95th percentile for age and height ([Appendix E](#); [NHBPEP 2005](#));
13. Has used monoamine oxidase-A (MAO-A) inhibitor, methysergide, methylergonovine, or cimetidine in the 2 weeks before randomization or an SSRI 4 weeks before randomization; if the patient has been on stable dose of SSRI for 8 weeks (2 months) prior to randomization, they may be included in the study.
14. Has any recent history of abuse (in the previous year) of alcohol or other drugs including drugs for the acute treatment of headache;
15. Is a female who is pregnant or breast-feeding;
16. Has severe hepatic impairment or any serious condition which, in the opinion of the investigator, would present a risk to the patient participating in the study;
17. Has a clinically relevant abnormality on nasopharyngeal examination as determined by the investigator; nasopharyngeal examination means a standard physical examination to rule out gross abnormalities of the nasopharynx and does not imply specialist examination prior to enrolling a patient.
18. Has a positive urine test for drug abuse not explained by the use of appropriately prescribed rescue medications.
19. Responds to the placebo challenge during the run-in period (ie, migraine headache intensity is mild or none at 2 hours after the placebo challenge).

For procedures for withdrawal of incorrectly enrolled patients, see Section 5.3.

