Serotonin syndrome has been reported with combined use of triptans, and selective serotonin re-uptake inhibitors (SSRIs) and serotonin norepinephrine re-uptake inhibitors (SNRIs). Serotonin Syndrome is a potentially life-threatening condition, and may include signs and symptoms such as: mental status changes (eg, agitation, hallucinations, coma), autonomic instability (eg, tachycardia, labile BP, hyperthermia), neuromuscular aberrations (eg, hyperreflexia, incoordination), and/or gastrointestinal symptoms (eg, nausea, vomiting, diarrhea). Careful observation of the patient is advised, if concomitant treatment with zolmitriptan and an SSRI or SNRI is given, particularly during treatment initiation and dosage increases.

All efforts will be taken to minimize risk to patients enrolled in this trial. No patient will be enrolled who has had a previous adverse reaction to zolmitriptan or other triptans. Patients with medical conditions that would put them at increased risk for adverse reactions will also be excluded from this study.

In order to ensure that the population enrolled in the study is representative of the patient population at large, individuals who have medically stable chronic conditions will not be excluded. These patients will not be required to stop their treatment for their chronic conditions (eg, high BP) prior to or during the trial. Of particular concern are those patients who are taking SSRI/SNRIs. Concomitant use of a triptan with an SSRI/SNRI has been associated with the Serotonin Syndrome. To minimize this risk, only patients who have been stabilized on an SSRI or SNRI for at least 2 months will be enrolled and no dosage

adjustments of these agents will be allowed. These patients will also be carefully monitored for any signs and symptoms of the Serotonin Syndrome.

Migraine in adolescents is a debilitating neurological condition. At present, only 2 triptan oral formulations (almotriptan and rizatriptan) are approved for acute treatment of migraine in adolescents. This trial will fully explore the efficacy and safety of zolmitriptan nasal spray as an alternative for the acute treatment of migraine. This single-attack trial is specifically designed to minimize risk to patients while potentially identifying a new treatment option for these patients.

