## 5. STUDY CONDUCT

### 5.1 Restrictions during the study

The following restrictions apply in this study during the placebo challenge and treatment period:

1. Patients must treat headache within 30 minutes of onset of moderate to severe headache pain reaching moderate or severe intensity.
2. Patients must be completely symptom-free from any previous headache.
3. Patients must initiate treatment of the migraine headache with only the study drug provided. The nasal spray device is for single use and will contain only 1 dose of study drug. If the migraine does not improve from moderate to severe to none or mild pain at 2 hours post dose, the patient has the option to use rescue medication. A 2nd dose of study drug will not be allowed as rescue medication, nor will it be provided. Rescue medications, as determined by the protocol and the investigator, may be taken 2 hours after taking the study drug and may include NSAIDS, anti-emetics, analgesics (eg, opioids), or sedatives. Rescue medication will not be provided by AstraZeneca.
4. Before taking the study drug, patients must not have:
  - Treated this headache with any other medication,
  - Received any ergotamine or ergotamine-like derivative (eg, dihydroergotamine, methysergide) or triptan (5HT1B/1D agonist) in the 24-hour period before treatment with the study drug,
  - Used opiates in the last 24 hours;
5. After taking the study drug, patients must not:
  - Sleep or nap for 2 hours,
  - Use rescue medication within 2 hours of taking the study drug (see above for use of rescue medication),
  - Use an ergotamine or ergotamine-like derivative (eg, dihydroergotamine, methysergide) or non-study triptans (5HT1B/1D agonist) for 24 hours.

Patients will be allowed to continue any medication being taken at the time of entry into the study (other than medication referred to above for the **acute treatment of migraine or**

**restricted medications noted in Section 5.6).** This includes medication normally taken for migraine prophylaxis or medication normally taken to control a long-standing condition, provided it is for a condition that is stable, and in the investigator's opinion, not adversely affected by participation in the study.

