## **5.2 Subject enrollment and randomization**

The Principal Investigator (PI) will:

1. Obtain signed informed consent from the patient's parent or guardian/legal representative and signed assent from the patient before any study-specific procedures are performed;
2. Assign potential patient a unique enrollment number, beginning with "E#";
3. Determine patient eligibility (see Sections 4.1 and 4.2);
4. Assign an eligible patient a unique randomization code (patient number), beginning with "#."

As patients are screened for the study, they must be allocated an enrollment code (E-code). The E-code is a 7-digit number made up of the center number and the patient number within that particular center.

If a patient withdraws from participation in the study, then his/her enrollment/randomization code cannot be reused.

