## **5.6 Concomitant and post-study treatment(s)**

The use of cimetidine and MAO-A inhibitors are not permitted. The dose of any SSRIs or migraine prophylactic agent must be stabilized within 2 months prior to randomization. If the patient has been on stable dose of SSRI for 8 weeks (2 months) prior to randomization, they may be included in the study. No triptan, ergotamine or ergotamine-containing medications may be used 24 hours before, concurrently, or after study drug. Opiates should not be used 24 hours before study drug treatment. NSAIDs, antiemetics, analgesics (eg, opioids), and

sedatives are permitted as rescue medications, as agreed by the treating physician, at  $\geq 2$  hours post study drug treatment.

Other medication, which is considered necessary for the patient's safety and well being, may be given at the discretion of the investigator permitting that this ongoing treatment won't be adversely affected by study participation, and recorded in the appropriate sections of the eCRF.

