## **5.8 Withdrawal from study**

Patients may be discontinued from the study in the following situations:

- Patient decision: Voluntary discontinuation by the patient or the parent/legal guardian who is at any time free to discontinue the patient's participation in the study, without prejudice to further treatment;

- Severe non-compliance to the study protocol as judged by the investigator and/or AstraZeneca;
- Incorrectly enrolled patients;
- Patient is lost to follow-up.
- The patient has a clinically significant or serious AE that would not be consistent with continuation in the study, as determined by the investigator, AstraZeneca or its representative, or the patient.
- Safety reasons as judged by the investigator, particularly if the patient becomes pregnant;
- The condition under investigation worsened.
- The patient is unable to comply with the restrictions on the use of concomitant medications as detailed in Section 5.6.
- The patient is unable to tolerate the assigned dose of study drug.

Patients are at any time free to withdraw from the study without prejudice to further treatment (withdrawal of consent). A patient that decides to withdraw from the study will always be asked about the reason(s) and the presence of any AEs. If possible, they will be seen and assessed by an investigator(s).

Patients who withdraw from the study will be required to complete Visit 3 (final visit/end-of-study) assessments at the ET visit. AEs will be followed up (see Sections 6.4.3 and 6.4.4); the nasal spray device and patient diaries used to collect data on migraine attacks and study drug should be returned by the patient. Patients who withdraw from the study will not be replaced.

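### The Section 1.4 serotonin-syndrome safeguard is only partly carried into the rules: exclusion 13 and Section 5.6 omit SNRIs, and neither repeats the bar on dose adjustments

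*Protocol*

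**What the plan says.** Section 1.4 of the protocol (Benefit/risk and ethical assessment) singles out patients on selective serotonin re-uptake inhibitors (SSRIs) or serotonin norepinephrine re-uptake inhibitors (SNRIs), because giving a triptan with either class has been linked to serotonin syndrome. It sets two conditions. On entry: "only patients who have been stabilized on an SSRI or SNRI for at least 2 months will be enrolled". After that, no dosage "adjustments of these agents will be allowed". It adds that these patients will be monitored carefully.

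The rules that a site applies are elsewhere:

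- Section 5.2 tells the investigator where eligibility is decided: "Determine patient eligibility (see Sections 4.1 and 4.2".
- Section 4.2, exclusion 13, excludes recent use of "an SSRI 4 weeks before randomization; if the patient has been on stable dose of SSRI for 8 weeks (2 months) prior to randomization", in which case the patient may be included.
- Section 5.6 says: "The dose of any SSRIs or migraine prophylactic agent must be stabilized within 2 months prior to randomization". It then repeats the 8-week SSRI allowance. It leaves other medication needed for the patient's "safety and well being, may be given at the discretion of the investigator", on condition that the ongoing treatment is not adversely affected by study participation.
- Section 5.1 says: "Patients will be allowed to continue any medication being taken at the time of entry into the study", apart from acute migraine drugs and anything Section 5.6 restricts. For long-standing conditions it requires that the condition be stable.
- Section 5.8 gives one medication-specific ground for withdrawal: a patient who is "unable to comply with the restrictions on the use of concomitant medications as detailed in Section 5.6".

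Section 3.1.3 allows up to 10 weeks from randomization to the treated attack.

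**The concern.** Section 1.4 presents the rule as the means by which the trial keeps a potentially life-threatening interaction in check. If the numbered criteria and the concomitant-medication section carry only part of it, a site can follow them faithfully and still randomize a patient whom the protocol's own safeguard keeps out. The same site has no instruction in Sections 5.1, 5.6 or 5.8 about a dose change made while the patient waits for an attack. The patients are 12 to 17 years old and dose themselves away from the clinic. What is at stake is patient safety and agreement between sections, not the primary comparison.

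**Working it through.** No arithmetic decides this point; it rests on setting the sections side by side.

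**Step 1: where each class is named.** Section 1.4 names SNRIs five times, always together with SSRIs. In Sections 4 and 5, SSRIs are named four times (two in exclusion 13 and two in Section 5.6) and SNRIs not once.

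**Step 2: when the stability windows end.** The 4-week and 8-week windows in exclusion 13 and the 2-month window in Section 5.6 all end at randomization. Dosing can follow up to 10 weeks (10 × 7 = 70 days) later.

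**Step 3: the possible cases.**

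| Case | Section 1.4 | Exclusion 13 | Section 5.6 |
|---|---|---|---|
| SSRI started or dose changed shortly before randomization | Kept out | Kept out | Kept out |
| SNRI recently started as migraine prophylaxis | Kept out | Silent | Kept out, as a prophylactic agent |
| SNRI recently started for another reason | Kept out | Silent | Silent |
| SSRI or SNRI dose adjusted between randomization and dosing | Not allowed | Window has ended | Window has ended; no rule |
| SSRI or SNRI newly started after randomization | No ban stated; careful observation advised | Window has ended | Investigator discretion, with a condition |

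The third and fourth rows are the mismatches: Section 1.4 rules the case out and neither operative section does. In the first row all three sections agree. In the second, Section 5.6 supplies what exclusion 13 omits. In the fifth, Section 1.4 contains no ban for the other sections to contradict.

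**Step 4: what remains for the two mismatches.** For the recent SNRI starter, the remaining protection is judgement: inclusion 12 (participation not harmful), exclusion 4 (a medical condition that raises risk with zolmitriptan), exclusion 16 (a serious condition that presents a risk) and the stable-condition proviso in Section 5.1. For the dose adjustment, the medication ground in Section 5.8 reaches only what Section 5.6 restricts, and Section 5.6 does not restrict it. The general grounds in Section 5.8, severe non-compliance and safety as judged by the investigator, remain.

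**The case against.** The strongest reply is that Section 1.4 is part of the same approved protocol and its wording is mandatory, so the bar on dose adjustments is stated once rather than absent, and nothing in Sections 4 or 5 permits what it forbids. The general clauses also give an attentive investigator room to act: a patient who has just begun an SNRI for a new or unstable condition does not fit comfortably within Section 5.1, and a dose increase before dosing could be handled under the safety ground in Section 5.8. Exposure is a single dose.

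Much of this stands, and it is why the point is minor. It does not remove the mismatch. Section 5.2 sends the investigator to Sections 4.1 and 4.2, not to Section 1.4. The stable-condition proviso concerns the illness, not how long the drug has been taken at a fixed dose. The protocol did not rely on general judgement for SSRIs, for which it wrote exclusion 13.

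A reader might infer more than the text supports, in three ways:

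- **That no operative rule restricts SSRI starts or dose changes at all before dosing.** Exclusion 13 and Section 5.6 do so up to randomization; for SSRIs the gap begins only there.
- **That Section 1.4 promises a ban on new starts after randomization.** It promises stability at enrollment, no dose adjustments and monitoring. On treatment initiation it advises careful observation.
- **That the 4-week interim visit is deficient because it has no medication check.** No section promises one, so its absence contradicts nothing.

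**Conclusion.** The point holds in two parts. First, the stability condition that Section 1.4 sets for both classes is applied in exclusion 13 and Section 5.6 to SSRIs only, with SNRIs reached only when taken for migraine prophylaxis. Second, the bar on dose adjustments appears nowhere outside Section 1.4, so it is missing from the rules that govern the up to 10 weeks between randomization and dosing.

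The size is small: a safety-consistency correction, with no effect on bias, power or the type I error rate. The protocol gives no number of SSRI or SNRI users, and the view that few patients are affected is an assumption. The conclusion also assumes that sites work from the numbered criteria and Section 5.6, as Sections 5.2 and 5.8 direct. It does not assume that Section 1.4 is non-binding, which the protocol nowhere says.

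**What to change.** In exclusion 13 and in Section 5.6, add 'or SNRI' after each mention of SSRI. In Section 5.6, add a statement that the SSRI or SNRI dose must not be adjusted between randomization and dosing, and that a patient who needs an adjustment should receive it and should not take study drug. Because Section 5.8 refers to Section 5.6, the medication ground for withdrawal then covers the rule without further change.

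The cost is a few words and one statement. A few recent SNRI starters would be excluded, which is what Section 1.4 already intends. A few attacks may go untreated with study drug; those patients would fall outside the full analysis set, which Section 12.1.2 limits to treated patients, and would add slightly to the 20% that Section 12.3 expects to drop out before treatment.

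The sponsor may also wish to bar new SSRI or SNRI starts after randomization, or to ask about medication at the interim visit. Both are optional additions and are not needed to bring the sections into agreement.
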